7.1. Trial intervention and dosing schedule

The trial intervention in IIH-Advance is Tirzepatide, self-administered weekly via a subcutaneous injector pen, plus standard of care (see Section 1.2). The dose will escalate over the 6-month intervention period in accordance with the dosing schedule detailed in the Summary of Product Characteristics for Tirzepatide and summarised below, although titration can be individualised according to patient tolerability. This titration should be followed each time the intervention is being introduced. At each timepoint that Tirzepatide is to be prescribed, the trial doctor will check the current dose is tolerated, and if so prescribe the next planned dose.

Please note that, since Tirzepatide is supplied in weekly injector pens, a month in IIH-Advance will be defined as 28 days.

- Month 1 dose 2.5 mg
- Month 2 dose 5 mg
- Month 3 dose 7.5 mg
- Month 4 dose 10 mg
- Month 5 dose 12.5 mg
- Month 6 dose 15 mg

If allocated to receive Tirzepatide, participants will be trained how to administer the drug. As per routine practice within the NHS and the wider NHS primary care use of Tirzepatide, a video instructing how to self-administer the injection will be shown to participants and then discussed with the Trial Researcher before any self-administration; this video will be available at all times through the IIH-Advance website.

7.2. Drug interaction or contraindications

7.2.1. Permitted medications/interventions

Other than the randomised allocation (and therefore with reference to **section 7.2.2** below), treatment as usual as per local practice (including weight management or weight loss regimes) will continue.

7.2.2. Prohibited medications/interventions

Any medication which is contraindicated in people taking Tirzepatide according to the British National Formulary will be prohibited, if appropriate according to the participant's allocation. Glucose-lowering medications are prohibited as per the eligibility criteria.

7.2.3. Pregnancy

Tirzepatide is contraindicated in pregnancy due to the lack of data in humans to determine the risk of birth effects, miscarriage, or other adverse outcomes. Tirzepatide is not recommended in women wanting to become pregnant and should be discontinued for one month before a planned pregnancy. If a participant becomes pregnant whilst allocated to Tirzepatide, they will be instructed to immediately stop taking it.

7.2.4. Contraceptives

Administration of a combination oral contraceptive in the presence of a single dose of Tirzepatide (5mg) led to a small reduction in combination oral contraceptive efficacy in normal weight women, but this was not considered to be clinically relevant and the Summary of Product Characteristics does not suggest adjustment of the dose of combination oral contraceptive is needed. In women with a high BMI, there is no data and reduced efficacy of oral contraceptives cannot be excluded. If using an oral contraceptive it is advised to switch to a non-oral contraceptive method or add a barrier method of contraception upon initiating Tirzepatide (for 4 weeks), or after each dose escalation (for 4 weeks)⁴⁵.

7.3. Intervention modification or discontinuation

It is expected that there may be cases where Tirzepatide is less well tolerated in terms of side effects. In this case, on discussion between participant and Trial Doctor, a dose may be reduced or held at the previous month's dose as required. The reason should be noted on the EDC Medication Form.

7.4. Intervention supply and storage

Tirzepatide will be prescribed by a Trial Doctor, using an online pharmacy (this will be QuickMeds unless there is an exceptional issue that would require moving to an alternative pharmacy to maintain drug supply). QuickMeds are a registered pharmacy (9012521) and a manufacturer-recommended (Eli Lilly) local supplier⁵⁹. A trial-specific section of the secure QuickMeds prescribing portal will be set up for Trial Doctors to prescribe in a process similar to prescribing in private practice.

Tirzepatide will be prescribed in accordance with the recommended dosing schedule, with modification or reduction as agreed between clinician and participant depending on tolerability. The medication will be dispensed and dispatched as per usual practice from QuickMeds once the online prescription is completed. A monthly repeat prescription will only be issued if the participant attends and completes the monthly follow up appointment to ensure safety and compliance.

No clinical trial specific pharmacy requirements of the drug intervention including supply, storage, labelling, drug accountability and destruction will be needed. The participant will be advised that Tirzepatide needs to be stored in their refrigerator and that after use the self-injector pen should be kept for visual inspection. Responsibility for drug dispensing will lie with QuickMeds pharmacy.

7.5. Adherence

During each monthly follow up appointment, the participant will be asked to produce the Tirzepatide pens prescribed over the last month, where they will be visually inspected for adherence by the Trial Researcher. Visual confirmation of used doses via the indicator window on the pen will be recorded on the EDC.

7.6. Standard of care

We are evaluating the impact of weight loss from Tirzepatide plus standard of care against current NHS practice (standard of care). Standard of care is described in the IIH guidelines (see also **Section 1.2**) and in medically treated patients encompasses giving dietary advice on weight loss, with or without the use of off label drugs which may lower ICP (for example, acetazolamide, frusemide, topiramate, amiloride and spironolactone)¹⁵. In patients with sight threatening IIH, a surgical intervention could be used to save vision (CSF shunting, optic nerve sheath fenestration and venous sinus stenting)¹⁵.

8. Outcome Measures

8.1. Main trial outcomes

8.1.1. Primary outcome

Resolution of papilloedema, as measured by OCT at 6 months post-randomisation.

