4.2. Exclusion criteria

- Previous bariatric surgery within the last 3 months or intention to undergo bariatric surgery during the trial.
- Previous surgery for IIH including optic nerve sheath fenestration, CSF shunting procedures, sub-temporal decompression and venous stenting.
- Using glucose-lowering medication.
- Currently taking or has received a GLP-1R agonist for any indication in the last 4 weeks.
- Previous or current pancreatitis.
- Contraindication to Tirzepatide (e.g. previous or current medullary cancer, history of multiple endocrine neoplasia, active gall stones).
- Current eating disorder requiring hospital intervention or treatment.
- Is unable to self-administer (or administer with carer support) the trial medication.
- Females of child-bearing potential only:

- Pregnant. Note: Spot urine test will be performed before randomisation to rule out pregnancy in females of child-bearing potential
- Not willing to take highly effective contraceptive measures during the study intervention period AND for 5 weeks following the last trial medication dose
- Not willing to stop breastfeeding once randomised into the trial

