9.4. Review and treatment allocation visit R2 (month 6)

With sufficient notice before the 6 month time point, an OCT scan will be arranged at a participating Specsavers UK store of the participant's choice, to be completed <2 weeks before the 6 month time point.

Then, at 6 months, a full review as per the baseline visit as detailed in **section 9.2** (minus height, demographics and medical history) will be carried out.

Once the OCT scan has been analysed by the trial researcher and all month 6 assessments have been completed, participants will be classed as responder, partial responder or non-responder.

- Responders to standard of care will leave the trial.
- Non-responders to Tirzepatide will proceed to their final follow up visit (**section 9.6**).
- Responders and partial responders to Tirzepatide, and partial and non-responders to standard of care will be re-randomised into R2 as per the R1 randomisation method in **section 6**.

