9.7. Unscheduled OCT visits

If there is deterioration (or suspected deterioration) of visual function, additional OCT visits should be scheduled with Specsavers to ensure the participant's ongoing visual health, as would be recommended in routine NHS practice. If required, an urgent referral to the NHS will be arranged and Tirzepatide halted.

10. Schedule of assessments

Table 1: Schedule of Assessments (Researcher completed)

Visit	0	1	R1				R2		SA3		Follow up 5 weeks after stopping intervention
	Screening	Baseline/ Randomisation	2-3 Months 1-2	4 Month 3	5-6 Months 4-5	7 Month 6	8-12 Months 7-11	13 Month 12	14-18 Months 13-17	19 Month 18	
Visit window (days)	(-14)	(+14)	(+/-7)	(+/-7)	(+/-7)	(+/-7)	(+/-7)	(+/-7)	(+/-7)	(+/-7)	(+/-7)
Eligibility check		x				x		x			
Valid informed consent	x										
OCT Imaging	x					x		x		x	
Ophthalmic review		x				x		x		x	
Medical, IIH and ophthalmic history*		x									
Concomitant medication		x	x	x	x	x	x	x	x	x	
Demographics		x									
Randomisation		x				x					
Height	x										
Weight and BMI	x	x	x	x	x	x	x	x	x	x	
Urine pregnancy test		x				x		x			
Safety and adverse events check			x	x	x	x	x	x	x	x	x
Fit and well check											x
Trial medication training		x				x		x			
Trial medication dispensing		x	x	x	x	x	x	x	x	x	
Trial medication adherence			x	x	x	x	x	x	x	x	

*assessed by Trial Doctor

NB: OCT imaging performed at local participating Specsavers UK store

Table 2: Schedule of Assessments (Participant completed)

Visit	0	1	2-3	4	5-6	7	R1		R2		SA3	
	Screening	Baseline/ Randomisation	Months 1-2	Month 3	Months 4-5	Month 6	Months 7-11	Month 12	Months 13-17	Month 18	14-18	19
Visit window (days)	(-14)	(+14)	(+/-7)	(+/-7)	(+/-7)	(+/-7)	(+/-7)	(+/-7)	(+/-7)	(+/-7)	(+/-7)	(+/-7)
CSRI		x	x	x	x	x	x	x	x	x	x	x
Headache Diary		x	x	x	x	x	x	x	x	x	x	x
HIT-6 questionnaire		x	x	x	x	x	x	x	x	x	x	x
WPAI		x				x		x				x
SF-36		x				x		x				x
EQ5D-5L		x				x		x				x
NEVI VFQ-25		x				x		x				x
Binge Eating Questionnaire		x				x		x				x
AUDIT		x				x		x				x
HADS		x				x		x				x
PSQI		x				x		x				x
ISI		x		x		x						
Berlin Questionnaire		x		x		x						
STOP-Bang		x		x		x						
Research biological sample collection		x		x		x		x			x	
Sleep / activity tracker (2 weeks prior)		x		x		x						

11. Withdrawal and changes in levels of participation

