12.4.2. Serious Adverse Events requiring non-expedited reporting to the Trial Office

Where the safety profile is well established, the causal relationship between the intervention (or the participant's underlying condition) and the SAE may be known. That is, such events are protocol-defined as "expected" (see **Section 12.5.2**). Such events should still be recorded by the trial team in the participant's notes field on the EDC, and reported to the Trial Office on the trial specific SAE form **within 4 weeks of becoming aware of the event**. These events do not require expedited reporting (i.e. immediately on becoming aware of the event) since the assessment of expectedness for the specified events has been pre-defined. These are:

- Hospitalisation due to exacerbation of IIH
- Hospitalisation for treatment of IIH

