16.2.1. Primary outcome

Resolution of papilloedema at the 6 month assessment. Where patients are missing the primary outcome (for example due to non-attendance at 6-month visit), they shall be treated as a failure and included in the denominator only (unless there is data from an unscheduled visits which could be utilised).

Resolution of papilloedema will be reported as n/N where n is the number of participants with resolution of papilloedema and N the total number of participants in the corresponding trial arm, and percentages as appropriate. Logistic regression model will be used to analyse the primary outcome. Risk ratio, risk difference and the associated 95% confidence intervals will then be derived using marginal standardisation method.

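### Surgery for IIH before the month-6 scan is not addressed in the primary outcome, so an operated participant whose swelling clears counts as a success for the allocated arm

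*Protocol*

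**What the plan says.** Protocol section 8.1.1 defines the primary outcome as "Resolution of papilloedema, as measured by OCT at 6 months post-randomisation". Section 3.1.1 classes anyone with resolution as a responder and adds no exception.

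Section 16.2.1 has one rule that turns a participant into a failure. If the outcome is missing, "they shall be treated as a failure and included in the denominator only", unless an unscheduled visit supplies usable data. Section 16.2.4 repeats the rule.

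Surgery during the trial is foreseen in three places:
- Section 7.6 describes standard of care, which both arms receive, and says that in sight-threatening IIH "a surgical intervention could be used to save vision".
- Section 9.7 covers visual deterioration: "If required, an urgent referral to the NHS will be arranged and Tirzepatide halted".
- Section 12.4.2 lists "Hospitalisation for treatment of IIH" among the pre-defined expected serious adverse events.

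At entry, section 4.2 excludes "Previous surgery for IIH including optic nerve sheath fenestration, CSF shunting procedures, sub-temporal decompression and venous stenting". The protocol has no matching rule for surgery after randomisation.

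Section 9.4 uses the month-6 class to route participants. "Responders to standard of care will leave the trial", while responders and partial responders to Tirzepatide, and partial and non-responders to standard of care, are randomised again.

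**The concern.** The primary objective (section 2.1.1) is the effect of weight loss induced by Tirzepatide. A shunt, fenestration or stent can clear disc swelling by another route. A participant who deteriorated enough to need surgery would then be recorded as a success for weight loss or for standard of care.

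Two things are at stake. The first is the primary comparison: operated and resolved controls shrink the difference, and operated and resolved Tirzepatide participants enlarge it. The second is stage R2. A Tirzepatide participant whose drug was halted and who was then operated on could enter the continue-versus-stop comparison (R2a/R2b) as a responder, where a working shunt could mask recurrence. An operated control with resolution would simply leave. These classes are assigned at the month-6 visit, so a later statistical analysis plan can change how the primary outcome is scored but cannot undo a re-randomisation.

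**Working it through.** **1. Following the text for one participant.** Take someone who deteriorates at month 3, has a CSF shunt, and shows resolution on the month-6 scan.
- Section 8.1.1: resolution on the scan, so a success.
- Section 16.2.1: the outcome is not missing, so the failure rule does not apply.
- Section 3.1.1: a responder.
- Section 9.4: leaves the trial if on standard of care; is re-randomised if on Tirzepatide.

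If the month-6 scan is missing, section 16.2.1 allows unscheduled data. Section 9.7 ties unscheduled scans to deterioration, so a post-operative scan could turn a default failure into a success.

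**2. The plan's own sample size (section 16.1).** Inputs: type I error 0.05, power 90%, 5% against 37%, 25% attrition. The protocol does not state sidedness; two-sided is taken here. With the mean rate (0.05 + 0.37)/2 = 0.21:

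n = [1.960 × √(2 × 0.21 × 0.79) + 1.282 × √(0.05 × 0.95 + 0.37 × 0.63)]² / 0.32² = 31.9, so 32 per arm.

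32 / 0.75 = 42.7, so 43 per arm. Both stated figures reproduce.

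**3. Weight of a single case.** Expected resolutions are 0.05 × 43 = 2.15 on standard of care and 0.37 × 43 = 15.9 on Tirzepatide, taken as 2 and 16. One participant is 1/43 = 2.3 points.

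| Standard of care | Tirzepatide | Risk difference | Risk ratio |
|---|---|---|---|
| 2/43 (4.7%) | 16/43 (37.2%) | 32.6 points | 8.0 |
| 3/43 (7.0%) | 16/43 | 30.2 points | 5.3 |
| 4/43 (9.3%) | 16/43 | 27.9 points | 4.0 |
| 2/43 | 17/43 (39.5%) | 34.9 points | 8.5 |
| 2/43 | 18/43 (41.9%) | 37.2 points | 9.0 |

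Rows two and three add one and two operated controls; rows four and five add one and two operated Tirzepatide participants.

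**4. Power, under an assumed rate.** The protocol gives no surgery rate. Suppose a share s of controls who would not otherwise resolve are operated on and all of them resolve, with no such cases on Tirzepatide. The control rate becomes 0.05 + 0.95s.

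| s (assumed) | Control rate | Power, 32 per arm | Power, 43 per arm |
|---|---|---|---|
| 0 | 5.0% | 90.1% | 96.6% |
| 2% | 6.9% | 84.6% | 93.5% |
| 5% | 9.75% | 74.2% | 86.1% |

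Section 16.2.1 keeps everyone in the denominator, so 43 is the number analysed. That column makes no allowance for missing scans scored as failures. The calculation also assumes that the 5% planning rate contains no surgical resolutions.

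**5. Would the event be captured?** The service-use items in section 8.1.2 (CSRI) are doctor and hospital attendance, days in hospital, lumbar punctures and brain imaging; surgery is not named. Section 12.4.1 exempts pre-planned admissions and hospital attendances under 24 hours from the serious adverse event form. Neither source is certain to yield the procedure and its date.

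**The case against.** The strongest reply is that this is a coherent choice and no error. The trial is pragmatic, compares against current NHS practice, and section 7.6 places surgery within that practice. Scoring the scan whatever usual care was received is a legitimate treatment-policy outcome. That reading is possible, but the protocol nowhere states it. It fits poorly with an objective about weight loss induced by Tirzepatide, and with labelling an operated participant a responder to the allocated arm.

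A second reply is that handling such events belongs in the statistical analysis plan, which is not shown here. That holds for the scoring of the primary analysis. It does not hold for the responder classes, which the protocol fixes and applies at the visit.

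Several objections to stronger readings stand:
- A reader might infer a serious loss of power. The documents do not support that. Section 4.1 keeps out sight-threatening papilloedema requiring urgent surgery, section 4.2 keeps out earlier IIH surgery, and section 1.2 calls surgery a last resort. The 2% to 5% range is an assumption, and the 5% control rate may already include surgical cases. Even 16/43 against 4/43 gives a Fisher exact p of 0.004.
- A reader might infer that operated participants certainly enter R2. Table 1 in section 10 schedules an eligibility check at month 6. Its content is not spelled out, but it may bear on someone who has now had an excluded operation.
- A reader might extend the point to bariatric surgery. That is a weight-loss treatment, not rescue for failing vision, and intention to have it during the trial is already excluded.
- Relabelling operated controls as non-responders throughout would send them into the delayed-start comparison (R2c). That would only move the problem.

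**Conclusion.** The gap is real and worth closing. As written, resolution after IIH surgery counts as a primary-outcome success and as response to the allocated arm, and nothing in the protocol says that this is intended.

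The likely size is small because the event is probably rare. Each operated and resolved control would add 2.3 points to an expected rate of about 2/43 and dilute the effect. Each such Tirzepatide participant would add 2.3 points in the other direction and inflate it. The power figures rest on an assumed surgery rate, on every operated participant resolving, and on a planning rate free of surgical cases.

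The documents do not support saying that the primary result would cease to reflect weight loss, or that R2 would certainly be contaminated.

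**What to change.** **Outcome.** In sections 8.1.1 and 16.2.1, state that CSF shunting, optic nerve sheath fenestration, sub-temporal decompression or venous stenting between randomisation and the month-6 scan is scored as non-resolution in the primary analysis, including where an unscheduled scan replaces the month-6 one. Report the scan-only result as a sensitivity analysis, and the number of procedures by arm. Leave bariatric surgery out of this rule; at most, report it by arm.

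**Data.** Add a field for procedure and date at the monthly visit.

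**Routing.** Keep this separate from outcome scoring. The sponsor should reconcile sections 7.6, 9.4 and 9.7 with the month-6 eligibility check in Table 1, so that operated participants form their own category and do not pass by default into R2a/R2b as responders or into R2c as non-responders. Their care stays with the clinical team.

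**Cost.** A few sentences and one data field. The sample size is unchanged if the planning rates contain no surgical resolutions. The small downside is that a rare participant who would have resolved without surgery is scored as a failure; the sensitivity analysis shows how much that matters.

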8.1.2. Secondary outcomes

All secondary outcomes measured at 6 months post-randomisation unless stated otherwise:

- Clinical outcomes:
 - Change in papilloedema as measured by OCT
 - Headache: Monthly headache days (MHD), Monthly migraine days, Headache responder rate ($\geq 50\%$ reduction in MHD), Monthly analgesic days and Monthly headache severity (numerical rating scale lowest 0-10 highest).
 - Headache disability (using the Headache Impact Test-6 (HIT-6))

- Weight and BMI
- Patient-centred outcomes:
 - Quality of Life (QoL) measured using the 36-item short form survey (SF-36) summary score, physical component score and mental component score
 - QoL measured using the EQ-5D-5L
 - Vision related QoL measured using the National Eye Institute Visual Function Questionnaire-25 (NEI-VFQ-25) plus the 10-item supplement
 - Binge eating measured using the Binge Eating Scale (BES)
 - Alcohol use measured using the Alcohol Use Disorders Identification Test (AUDIT)
 - Anxiety and depression measured using the Hospital Anxiety and Depression Scale (HADS)
 - Tolerability of weight loss in IIH driven by Tirzepatide as determined by all cause discontinuation at 6, 12 and 18 months
- Service use outcomes:
 - Service use (doctor attendance, hospital attendance, days in hospital, lumbar punctures, brain imaging scans) (as recorded by Client Service Receipt Inventory (CSRI))
 - Medication use (use and dose of acetazolamide or other ICP lowering drugs)
 - Absenteeism and presenteeism measured using the Work Productivity and Activity Impairment (WPAI) Scale

8.1.3. Exploratory outcomes

All exploratory outcomes measured at 12 and 18 months from baseline unless stated otherwise and assessed in a subset of participants:

- Clinical outcomes:
 - Resolution of papilloedema as measured by OCT
 - Change in papilloedema as measured by OCT
 - Headache: Monthly headache days, Monthly migraine days, Headache responder rate ($\geq 50\%$ reduction in MHD), Monthly analgesic days and Monthly headache severity (numerical rating scale lowest 0-10 highest).
 - Headache disability (using the HIT-6)
 - Weight and BMI
- Patient-centred outcomes:
 - Quality of life (QoL) measured using the SF-36 summary score, physical component score and mental component score
 - QoL measured using the EQ-5D-5L
 - Vision related QoL measured using the NEI-VFQ-25 plus the 10-item supplement
 - Binge eating measured using the BES
 - Alcohol use measured using the AUDIT
 - Anxiety and depression measured using the HADS
- Economic outcomes:
 - Service use (doctor attendance, hospital attendance, days in hospital, lumbar punctures, brain imaging scans) (as recorded by CSRI)
 - Medication use (use and dose of acetazolamide or other ICP lowering drugs)

- Absenteeism and presenteeism measured using the WPAI
- Sleep outcomes:
 - Sleep, circadian cycle and daytime activity will be evaluated at baseline, 3 and 6 months using wearable device actigraphy data and the Pittsburgh Sleep Quality Index, Insomnia Severity Index, Berlin questionnaire and STOP-Bang sleep apnoea screening questionnaire

Exploratory mechanistic outcomes

- Blood, saliva, 24-hour urine and stool samples will be collected at baseline, 3 and 6 months for later analysis for miRNA biomarkers, steroid metabolomics, protein biomarkers, inflammatory markers and Calcitonin Gene-Related Peptide, and rRNA sequencing to analyse gut microbiome changes.

Exploratory sleep sub-study outcomes

- Sleep, circadian cycle and daytime activity will be evaluated at baseline, 3 and 6 months.

Qualitative sub-study outcomes

A qualitative sub-study will answer the following research questions:

- What is the experience of weight management services and strategies for people with IIH?
- What should an optimal IIH weight management service look like?

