3.3. Sub-studies

- A mechanistic sub-study will collect biofluids (saliva, blood, 24-hour urine and stool) for evaluation of weight-loss related changes in liver function, diabetic status, hormones, markers of inflammation, pain chemicals involved in headache, and microRNA. Stool samples will be collected to evaluate the gut microbiome. Samples will be collected at baseline, 3 and 6 months. Please see **section 17** for full details.
- A qualitative sub-study will conduct two focus group discussions with main trial participants to explore acceptability of weight management strategies and the experience of people living with IIH and their weight management discussions with healthcare professionals. Please see **section 18** for full details.
- A sleep sub-study will use a wearable device to explore IIH, weight loss, and the circadian cycle and daytime activity.

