9.3. Monthly follow up visits (month 1-5, 7-11, and 13-17)

Monthly after randomisation the participant will be invited to attend a video call with a trial researcher to review weight, headache, and intervention compliance. These video calls will last approximately 30-60 minutes and include:

Researcher collection of:

- Weight (as demonstrated during the videocall or by photograph of the provided scales)
- Visual inspection of Tirzepatide pen (if participant randomised to receive Tirzepatide)
- Concomitant medications
- Participant's monthly headache history
- Postage of sample collection kit to participant (prior to months 3 and 6)
- Postage of exploratory sleep wearable device (months 3 and 6)

Participant completion of:

- CSRI
- HIT-6
- Blood, saliva, 24-hour urine and stool samples (sent prior to months 3 and 6)
- Two weeks of exploratory sleep wearable device actigraphy collection, two weeks of daily sleep diary (months 3 and 6)

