17.1. Sample collection

Before baseline, 3 month, and 6 month appointments, a sample kit will be posted to participants. This will consist of separate kits for:

- Blood – a capillary blood sampling kit will be provided for the collection of approximately 0.5ml of blood for processing into plasma, and another for approximately 0.5ml of blood for processing into serum. Participants will be requested to fast from midnight (water only) on the day of sample collection.
- Saliva – a swab and prepared tube will be provided for the collection of approximately 1 swab of saliva and 2ml of saliva drool. Participants will be requested to fast from midnight (water only) on the day of sample collection. Participants will also be requested to provide a saliva sample on a day they self-rate as a severe headache day, and another on a good headache day.
- Urine – a kit will be provided for a 24-hour urine collection, of which approximately 20ml of urine will then be sampled and collected for trial use.
- Stool – a kit will be provided for the collection of approximately 1g of stool.

Kits will include secure postage containers to send the samples to the UoB Biomedical Sciences Laboratory.

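### Table 2 schedules no month-3 PSQI although Section 8.1.3 sets one, and it marks a month-12 biological sample that the text does not plan

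*Protocol*

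**What the plan says.** **Sleep.** Section 8.1.3 puts the sleep evaluation "at baseline, 3 and 6 months using wearable device actigraphy data and the Pittsburgh Sleep Quality Index", followed by the ISI, Berlin and STOP-Bang: four questionnaires on one schedule. Section 9.2 lists all four at baseline. Section 9.4 repeats the baseline review at month 6, less height, demographics and medical history. Section 9.5 asks for full assessments as at baseline at month 12 and again at month 18.

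For the monthly calls, Section 9.3 lists "Two weeks of exploratory sleep wearable device actigraphy collection, two weeks of daily sleep diary (months 3 and 6"), but none of the four questionnaires.

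Section 10, "Table 2: Schedule of Assessments (Participant completed"), marks the ISI, Berlin, STOP-Bang and tracker at baseline, month 3 and month 6. Its PSQI row is marked at baseline, month 6, month 12 and a final column.

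**Biological samples.** Four sections of text agree on three rounds:
- Section 3.3: "Samples will be collected at baseline, 3 and 6 months".
- Section 8.1.3: "Blood, saliva, 24-hour urine and stool samples will be collected at baseline, 3 and 6 months for later analysis".
- Section 9.3: "Postage of sample collection kit to participant (prior to months 3 and 6").
- Section 17.1: "Before baseline, 3 month, and 6 month appointments, a sample kit will be posted to participants".

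The Table 2 row "Research biological sample collection" is marked at baseline, month 3, month 6 and month 12, with one further mark to the right.

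**The concern.** Research staff and those who build the data capture system usually work from the schedule table and the visit lists, not from the outcomes section. Here neither leads them to give the PSQI at month 3. A questionnaire about sleep at a given time cannot be filled in later, so a missed month-3 PSQI cannot be recovered. The month-3 actigraphy, sleep diary and other three sleep scales would then have no PSQI to set beside them.

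The sample row errs in the other direction. A month-12 round of capillary blood, saliva, 24-hour urine and stool would burden participants at a time for which no outcome is stated and no kit is posted. Section 5.7 makes both sub-studies a non-optional part of consent, so each discrepancy applies to everyone who reaches the visit and not to a volunteer subset.

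**Working it through.** No sample size or power formula bears on this. The check compares the marks in Table 2 with the text.

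**Step 1: sleep measures, Section 8.1.3 against Table 2**

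| Measure | Section 8.1.3 | Table 2 |
|---|---|---|
| PSQI | baseline, 3, 6 | baseline, 6, 12, final column |
| ISI | baseline, 3, 6 | baseline, 3, 6 |
| Berlin | baseline, 3, 6 | baseline, 3, 6 |
| STOP-Bang | baseline, 3, 6 | baseline, 3, 6 |
| Tracker (actigraphy) | baseline, 3, 6 | baseline, 3, 6 |

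The PSQI row has the same pattern as HADS, SF-36 and WPAI, which are due at baseline and the six-monthly reviews. This suggests that the row was filled in with the wrong group.

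**Step 2: size of the gap.** Section 8.1.3 implies 4 questionnaires × 3 times = 12 assessments per participant. Table 2 schedules 3 × 3 + 2 = 11 of them. The missing one is the month-3 PSQI, which is 1 of 3 PSQI time points. With 86 participants randomised, up to 86 forms are not scheduled; fewer people would reach month 3 after withdrawals.

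**Step 3: does other text supply the month-3 PSQI?** Section 9.2 covers baseline, 9.4 covers month 6 and 9.5 covers months 12 and 18. Only 9.3 covers month 3, and it is silent on all four questionnaires. For the ISI, Berlin and STOP-Bang, Table 2 makes good that silence. For the PSQI nothing does.

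**Step 4: PSQI after month 6.** Section 8.1.3 stops all four questionnaires at month 6. Section 9.5, read with 9.2, continues all four at months 12 and 18. Table 2 continues the PSQI and stops the other three. The three places give three different schedules.

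**Step 5: samples.** The text gives 3 rounds (baseline, 3, 6). The part of Table 2 that can be read with confidence gives 4 (baseline, 3, 6, 12).

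**Step 6: how far Table 2 can be trusted.** In the text available for this check, the right-hand end of the table is damaged. The header has 9 readable columns after screening (baseline, 1–2, 3, 4–5, 6, 7–11, 12, 13–17, 18), yet the CSRI row carries 11 marks. From screening to month 12 the cells line up across neighbouring rows. The blank PSQI cell at month 3 and the sample mark at month 12 both lie in that part. The last sample mark does not, and it does not line up with the last PSQI mark either, so no weight is put on it.

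**The case against.** Four arguments can be made against the point.

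- **It is small.** The PSQI is still taken at baseline and month 6. The other sleep measures are scheduled at month 3, and Section 16.2.2 summarises exploratory outcomes descriptively. This stands. A reader might infer that a stated outcome is lost altogether; the documents do not support that, because only one interim time point of one instrument is missing.
- **Section 9.3 is a generic list.** It serves 15 monthly calls (months 1–5, 7–11 and 13–17), says only what the calls include, and does not claim to override Table 2. This stands too. A reader might infer that all four questionnaires are dropped at month 3, but silence in a non-exhaustive list is not a deletion. It means only that 9.3 does not rescue the PSQI.
- **The table is damaged.** This holds for the right-hand end. A reader might count five sample marks and set three rounds against five; the fifth mark cannot be relied on. A shift of columns would not, however, leave the ISI, Berlin and STOP-Bang rows correct while moving only the PSQI.
- **Stray sample marks may do nothing.** Samples depend on posted kits, and four sections agree on when kits go out, so a month-12 round might never happen. The translational objective in Section 2.1.3 also sets no month-6 limit. Both points lessen the likely harm, but the table and the text still disagree.

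It is also tempting to call the later PSQI marks plain errors and delete them. Section 9.5 supports them, so deletion alone would create a new conflict.

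**Conclusion.** The point holds as an inconsistency in the schedule of exploratory assessments. As Table 2 stands, the month-3 PSQI set by Section 8.1.3 would be collected from no participant: 1 of 3 time points of one instrument, unrecoverable once the visit has passed. Table 2 also carries at least one sample mark after month 6, at month 12, against four sections that end at month 6.

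This rests on the cells from screening to month 12 being correctly placed, which their agreement across rows supports. It also assumes that Section 8.1.3 states the intended sleep schedule. The matching rows for the other three questionnaires make that likely but do not prove it. The primary and secondary outcomes, the sample size and the power are not affected. The correction is worth making because it is cheap, but the matter is minor.

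**What to change.** 1. In Table 2, mark the PSQI at month 3. In Section 9.3, name the PSQI, ISI, Berlin and STOP-Bang as month-3 items. If leaving out the month-3 PSQI was deliberate, say so in Section 8.1.3 instead.
2. Decide whether sleep questionnaires are wanted at months 12 and 18, and make Section 8.1.3, Section 9.5 (with its reference to 9.2) and Table 2 agree for all four. Do not simply delete the later PSQI marks.
3. Delete the sample mark or marks after month 6 from Table 2, or add the later rounds to Sections 3.3, 8.1.3 and 17.1 and to the kit posting in 9.3. Check the last mark in that row against the original table.

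The cost is an editorial amendment and one short questionnaire at a visit already held. If the late sample marks go, collection burden can only fall.
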